3.5.2.8 Vital Signs

Vital signs will be collected to include body temperature, blood pressure, respiratory rate, and heart rate. In each subject, the same arm will be used to collect all blood pressure readings, and every attempt will be made to use the same equipment and investigator/designee at each visit.

3.5.2.9 Physical Examination

The investigator will perform a physical exam to include a gross neurological exam and major body systems. The exam will focus on systems and organs known to be affected by hypoplasminogenemia.

3.5.2.10 Antibodies to Plasminogen

A blood sample will be obtained, centrifuged, and resulting serum sample transferred to and frozen in a cryovial, stored at -20°C, and shipped frozen to a Central Laboratory for detection of anti-plasminogen antibodies. Testing for anti-plasminogen antibodies is performed by ELISA. If neutralizing antibodies are suspected based on the plasminogen activity levels, an assay for assessing binding versus non-binding antibodies will be implemented. Details on processing and shipping of blood samples are provided in the Laboratory manual. For each sample taken for Plasminogen antibody testing in Segments 1, 2, and 3 a backup sample will also be taken and stored at the Central Laboratory facility in case of repeat testing requirements. No backup sample is needed at the End of Study visit for subjects who decide to enter the treatment protocol.

3.5.2.11 Virology

Screening serology testing will be conducted for HIV-1, HIV-2, HCV, HBV, HAV, and B19 (Appendix 15.2). Provided the subject meets all inclusion/Exclusion criteria, the subject may begin IMP infusion in Segment 1 or 2 without waiting for the virology results. Retention samples for virology at baseline will be tested with PCR.

3.5.2.12 Subject Diary

A diary will be provided to subjects during Segments 2 and 3 to record hypoplasminogenemia symptoms, IMP administration and any AEs between visits. The diary will be reviewed by the study personnel at each visit. Subjects will return the diary at the End of Study visit or Safety Follow-Up visit.

3.5.2.13 Clinical Assessments

All subjects will be clinically evaluated by the investigator for the clinical manifestation and severity of hypoplasminogenemia at the time points specified in the Schedule of Events table.

Measurement of Visible Lesions

The size (length and width) of visible lesions, such as ocular and gingival lesions, in subjects who have ligneous conjunctivitis will be measured and documented using photography at each visit. The procedure of photographic measurements is described in the Study Manual.

Imaging

Nonvisible lesions (ureteral, oropharyngeal, and bronchial) may be qualitatively evaluated as appropriate via imaging studies, such as computed tomography (CT) scans, X-ray, or other suitable imaging techniques at the Investigator's discretion. For example, if there is lung involvement suspected, lesions may be monitored via a CT scan obtained at Screening (unless already available within the past 6 months) and at the Week 12 visit, and at other time points if warranted.

Functionality Testing

Spirometry may be performed in subjects who have respiratory tract involvement of hypoplasminogenemia, if deemed appropriate by the investigator. The spirometry will measure forced expiratory volume in 1 second (FEV1), forced vital capacity (FVC), peak expiratory flow (PEF), and FEV1/FVC ratio. If applicable, these tests may be performed at Screening and Baseline (before the first dose of IMP), and every 4 weeks subsequently. However, no testing beyond Baseline is warranted if the subject's lung function is within normal limits at Screening and/or Baseline. Spirometry does not need to be repeated at Baseline if Screening is within 3 weeks of Baseline. Other functional tests appropriate for the affected organ system may be performed and analyzed as determined by the PI.

3.5.2.14 Clinical Global Impression – Global Improvement (CGI-I) Scale

The Clinical Global Impression-Global Improvement (CGI-I) Scale is a single, clinician-completed scale designed to capture the clinician's impression of the subject's disease improvement over time (Appendix 15.3). Clinicians are asked to consider their experience in this patient population and rate the change relative to the subject's state at baseline using a 7-point scale (1 = very much improved, 7 = very much worse).

3.5.2.15 Quality of life assessment

Subjects are asked to rate their overall quality of life using a 10-point scale (0 = non-functioning, 10 = normal; Appendix 15.4), adapted from a scale developed by the American Chronic Pain Association.

3.6 Stopping Rules and Withdrawal

3.6.1 Study Termination

The sponsor and/or a principal investigator may elect to terminate the study early as defined by the clinical trial agreement.

Any decision to voluntarily suspend or terminate a clinical trial will be carefully reviewed and fully justified. The sponsor will notify the FDA and the IRB of any suspension or termination, along with justification for restarting or terminating the study as applicable.

3.6.2 Stopping Rules

Any subject who experiences any of the following occurrences will suspend the IMP treatment until further assessments:

- Anaphylactic response to study drug administration
- A significant AE that, in the investigator's opinion, necessitates suspension of treatment
- Confirmed presence of neutralizing antibodies (in at least 2 measurements) in association with diminished plasminogen activity that obviates the potential benefit of plasminogen replacement therapy.
- Thrombotic or uncontrolled bleeding event requiring hospitalization

The SMC will review safety data on an ongoing basis and will determine if a subject should stop treatment, or if there are unforeseen events (e.g., thromboembolic event) that would warrant halting or stopping the study. Such events will be discussed with FDA before enrolling further subjects.

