	
given instructions for how to document receipt of IMP and how to return all used IMP vials.
 
Subjects at the Norway site in Segment 3 should return to the study site for a Safety Follow-up visit 30 days after the final IMP dose.
 
Due to the delay in product approval, subjects at the United States (US) site in Segment 3 will be allowed to enroll in Treatment Protocol 2002C018G and continue ongoing IMP treatment without any break in treatment. If subjects decide to enter Treatment Protocol 2002C018G, then they will return to the study site and complete the End of Study visit and sign an informed consent/assent for that study and stop participation in the current study. If subjects decide to not enter Treatment Protocol 2002C018G, then they will stop IMP and return to the study site for a Safety Follow-up visit 30 days after the final IMP dose.
 
Stopping rules
 
Any subject who experiences any of the following occurrences will suspend the IMP treatment until further assessments:
 
 • Anaphylactic response to study drug administration • A significant AE that, in the investigator’s opinion, necessitates suspension of treatment • Confirmed presence of neutralizing antibodies (in at least 2 measurements) in association with diminished plasminogen activity that obviates the potential benefit of plasminogen replacement therapy • Thrombotic or uncontrolled bleeding event requiring hospitalization 
The SMC will review safety data on an ongoing basis and will determine if a subject should stop treatment, or if there are unforeseen events (e.g., thromboembolic event) that would warrant halting or stopping the study. Such an event will be discussed with FDA before enrolling further subjects.

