Blood samples will be drawn and analyzed for plasminogen activity and plasminogen antigen levels at a Central Laboratory using validated assays. Plasminogen activity is assessed with a chromogenic assay developed and validated at a central specialty laboratory. Plasminogen antigen levels are determined by ELISA (Cell Sciences) and validated at a central specialty laboratory. For each sample taken for Plasminogen activity and antigen testing in Segments 1, 2, and 3 a backup sample will also be taken and stored at the Central Laboratory facility in case of repeat testing requirements. No backup sample is needed at the End of Study visit for subjects who decide to enter the treatment protocol.

Segment 1

Blood samples are drawn on Day -4 before the IMP infusion to establish baseline levels for plasminogen activity, antigen, and D-dimer and at the following time points after the end of the infusion: between 5 and 15 minutes, 6 hours (± 30 minutes), 24 hours (± 2 hours, Day -3), 48 hours (± 2 hours, Day -2), 72 hours (± 2 hours, Day -1), and 96 hours (± 2 hours, Day 0). An individual PK profile will be developed based on these time points.

Subjects who have had individual PK profile for 6 mg/kg Plasminogen with the sponsor, due to participation in the prior Phase 1 study, do not participate in Segment 1.

Segment 2

For subjects who do not undergo Segment 1, blood samples are drawn to measure plasminogen activity and antigen levels on Week 1, Day 0, before the first dose of the IMP is given, to establish the baseline levels.

For all subjects, blood samples will be drawn every 2 weeks before IMP infusion to measure trough levels through the final dose.

A full PK profile will also be done for all subjects at the end of Segment 2 (Week 12 visit) to evaluate the stability of individual PK profile after 12 weeks of IMP administration. As plasminogen is a consumable clotting factor, if significant lesion burden is present at the start of the study or if neutralizing antibody develops, a subject's PK profile may be altered by the end of the 12-week treatment period. At the Week 12 visit, blood samples are drawn before the IMP infusion and at the following time points after the end of the infusion: between 5 and 15 minutes, 6 hours (± 30 minutes), 24 hours (± 2 hours), 48 hours (± 2 hours), 72 hours (± 2 hours), and 96 hours (± 2 hours). The PK profile will be developed for each subject and compared with his or her prior PK profile(s).

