Furthermore, additional PK analyses may be performed at other time points during Segment 2 as needed, such as when a subject's trough level or antibody test suggests the appearance of neutralizing antibody against the IMP or when the dosing frequency has changed.

Segment 3

Blood samples will be drawn at each study visit every 3 months before IMP infusion to measure trough levels. Plasminogen activity and antigen, D-dimer spot levels will be measured at the End of Study visit for subjects who decide to enter Treatment Protocol 2002C018G.

PK Sample Handling:

Blood samples will be obtained, centrifuged, and resulting plasma will be transferred to, and frozen in a cryovial and stored at -20°C . All samples will be shipped frozen to a Central Laboratory for analysis. Details on processing and shipping of blood samples are provided in the Laboratory Manual.

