6.3.2 Pharmacokinetic/Pharmacodynamic Analysis

The primary endpoint is the number and percentage of subjects who achieve the target plasminogen activity trough levels for at least 3 measurements in 12 weeks during Segment 2. Primary endpoint success is defined as at least 80% of evaluable subjects (i.e., 8 or more) achieving the target trough levels for at least 3 measurements in 12 weeks. The target trough level is defined as an increase in plasminogen activity level of at least an absolute 10% (10 U/dL) from the subject's individual baseline level. Baseline is defined as the plasminogen activity level measured before the first dose of IMP at Segment 1, Day -4 for subjects who undergo Segment 1 or at Segment 2, Day 0 for those who do directly enter Segment 2.

The secondary PK endpoints include individual PK profiles at the end of Segment 2, compared with their PK profiles at baseline, and trough plasminogen activity and antigen levels during Segment 2 and Segment 3.

Plasminogen activity and antigen levels will be presented by individual subjects and summarized descriptively (number of subjects, mean, standard deviation [SD], coefficient of variation [CV], median, minimum, maximum, geometric mean and associated CV). Individual and median profiles of the concentration-time data will be plotted using nominal times. Median profiles may be presented on both linear-linear and linear-log scales.

Standard PK parameters, including area under the curve (AUC), clearance (CL), mean residence time (MRT), volume of distribution (V_d) and terminal half-life ($t_{1/2}$) will be calculated using non-compartmental analysis and baseline-adjusted plasminogen activity levels derived from Segment

1 data and, if a subject is suspected to develop neutralizing antibody to the IMP, plasminogen activity levels at the end of Segment 2.

Additional PK compartmental analysis may be performed and best-fit model will be used for further individual PK prediction.

The summary statistics will include the number of subjects, mean, median, standard deviation, minimum, and maximum. The PK parameters will be summarized with the geometric mean and 95% confidence interval around the geometric mean

D-dimer is monitored as a potential pharmacodynamic marker to better understand if there is a relationship between the levels of D-dimer in subjects over time and the subject's potential response to therapy.

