15.2 Clinical Laboratory Tests

Hematology	red blood cell count (RBC), white blood cell count (WBC), platelets, hemoglobin, and hematocrit
Biochemistry	albumin, AST, ALT, ALP, creatinine, blood urea nitrogen (BUN), lactate dehydrogenase (LDH), and bilirubin
Urinalysis	protein, albumin, and RBC; pregnancy test (female of child-bearing potential only)
Fibrinolysis/ coagulation	
Fibrinolysis panel:
 
 • D-dimer* • Alpha 2-antiplasmin (chromogenic assay) • Fibrin monomer (hemagglutination) • Alpha-1-antitrypsin 
Coagulation panel:
 
 • Prothrombin time (PT) • Partial thromboplastin time (PTT) • International normalization ratio (INR)
Immunogenicity	anti-plasminogen antibody
Pharmacokinetic and trough level sampling*	
 • Plasminogen antigen and activity levels • D-dimer*
Virology	
 • At screening, serology for HIV-1, HIV-2, HCV, HBV, parvovirus B19, and HAV. • At the End-of-Treatment visit, serology and PCR for HIV-1, HIV-2, HCV, HBV; PCR for B19 and HAV. • 30 days after last IMP dose (in Segment 2 or 3): serology and PCR for HIV-1, HIV-2, HCV, HBV; PCR for B19 and HAV.

*D-dimer is measured as part of the fibrinolysis panel and along with plasminogen trough level or PK level.

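### Section 3.5.2.10 names the wrong property for the follow-up antibody assay, so neither named antibody test can confirm the neutralizing antibodies that the suspension rule requires

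*Protocol*

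**What the plan says.** Protocol Section 3.6.2 lists four events that suspend a subject's treatment pending further assessment. One of them is "Confirmed presence of neutralizing antibodies (in at least 2 measurements) in association with diminished plasminogen activity that obviates the potential benefit of plasminogen replacement therapy". The synopsis gives the same rule.

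Protocol Section 3.5.2.10 describes the antibody testing. The routine test is stated as "Testing for anti-plasminogen antibodies is performed by ELISA". A second test is conditional: "If neutralizing antibodies are suspected based on the plasminogen activity levels, an assay for assessing binding versus non-binding antibodies will be implemented". The section refers to the Laboratory Manual only for sample processing and shipping. It also provides for a stored backup of each antibody sample taken in Segments 1 to 3.

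Under immunogenicity, Appendix 15.2 lists only "anti-plasminogen antibody". Section 1.4 says it is not known whether antibodies to the product would be neutralizing, and undertakes to assess their effects during the study.

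**The concern.** The suspension rule asks a functional question: does the antibody block plasminogen? The follow-up assay, as named, asks a different one: does the antibody bind? An antibody can bind without neutralizing, and a positive ELISA already shows binding. So the extra assay, at the point where neutralization is suspected, would not return the result that the rule needs.

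A site with an ELISA-positive subject and falling troughs could then err either way. It could continue treatment because neutralization was never confirmed, or suspend it because of an antibody that merely binds. The second error also matters, since Section 1.1.2 says no plasminogen replacement product is approved in the US.

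**Working it through.** No formula applies to the main point. The check sets what the rule needs beside what each named measurement gives.

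1. **What the rule needs.** Section 3.6.2 joins two conditions: neutralizing antibodies confirmed in at least 2 measurements, and activity reduced so far that therapy no longer offers benefit. Both must hold.

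2. **Routine ELISA (Section 3.5.2.10).** It detects anti-plasminogen antibodies. It is not stated to measure inhibition.

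3. **Conditional assay (Section 3.5.2.10).** As named, it sorts antibodies by binding. It is not stated to measure inhibition either. Antibody tests named: 2. Stated to measure neutralization: 0.

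4. **Activity and antigen levels (Section 3.5.2.6).** Low activity cannot confirm the antibody condition. It is what triggers the conditional assay, and it is already the rule's separate second condition, so using it a third time would be circular. Activity falling relative to antigen is more informative, but it is still inference about the antibody and not a measurement of it.

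5. **Extra PK.** Section 3.5.2.6 allows further PK analyses in Segment 2 when a "trough level or antibody test suggests the appearance of neutralizing antibody against the IMP". Section 6.3.2 derives PK parameters at the end of Segment 2 "if a subject is suspected to develop neutralizing antibody to the IMP". Both start from a suspicion and do not settle it. Section 3.5.2.6 also says the PK profile may change by Week 12 "if significant lesion burden is present at the start of the study or if neutralizing antibody develops", so a changed profile is not specific to antibody.

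6. **Deferral elsewhere.** Section 3.5.2.10 leaves no choice of assay to the Laboratory Manual. The test that confirms a subject-level suspension criterion is also not something a protocol would leave to a statistical analysis plan.

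**Size, by counting**
- Suspension criteria in Section 3.6.2: 4. Criteria that depend on neutralizing antibodies: 1.
- Subjects to whom the rule can still apply, from the status at 14 December 2017 in the clinical experience section: 15 enrolled − 3 completed in Norway = 12, and 12/15 = 80%. This is an upper bound on who is under the rule, not on who is at risk, because US subjects may leave for the separate treatment protocol or stop the product.
- The protocol gives no rate of ELISA-positive samples with reduced activity, so the number of subjects who would meet the criterion cannot be estimated.

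**The case against.** The strongest reply is that this is an erratum. The sentence opens with a suspicion of neutralizing antibodies, so its purpose is clear. An assay for antibodies that do not bind is hardly workable, and a central laboratory would probably query it. That is a fair reading, and the phrase is probably a slip. It also follows that the error lies in Section 3.5.2.10; the criterion in Section 3.6.2 is coherent and matches the synopsis. But the words are operative, they stand where the distinction matters, and no other section corrects them.

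A second reply is that the indirect evidence is good. Activity and antigen are measured together at each trough, and the lesion-burden explanation concerns burden at study start. In the interim data 13 of 14 visible lesions had resolved by Week 12, which makes that explanation weaker in long-treated subjects. This stands as far as it goes, but it does not remove the circularity in using low activity to confirm the antibody condition.

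A third reply is that subjects are protected in other ways. Suspension is provisional. The investigator can suspend treatment for a significant adverse event (Section 3.6.2) or withdraw a subject on medical grounds (Section 3.6.3). The Safety Monitoring Committee can stop a subject's treatment (Section 3.6.2) and reviews laboratory data and trough levels, although only periodically in Segment 3 (Section 3.7). This stands, and it limits the safety effect.

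**Conclusion.** The point holds as an error in Section 3.5.2.10 that leaves one of four suspension criteria without a direct test of its antibody condition. It should be corrected. It affects that criterion, for at most 12 continuing subjects, and the interpretation of any subject in whom neutralizing antibody is suspected. The conclusion takes the assay's name at face value; if the laboratory in fact runs a functional inhibition assay, only the wording is wrong.

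A reader might infer more than the protocol supports:
- **That a wrong assay has been or will be run.** The protocol says only that an assay will be implemented. It fixes no method and reports no such test.
- **That the immunogenicity conclusions for all 15 subjects are undermined.** The follow-up assay is conditional, Section 6.3.4 plans only to report subjects with changes in immunogenicity tests, and no endpoint is defined on neutralization.
- **That subjects losing benefit cannot be stopped.** The other grounds for stopping do not depend on this assay.

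**What to change.** In Section 3.5.2.10, replace the binding versus non-binding phrase with neutralizing versus non-neutralizing antibodies, measured as inhibition of plasminogen activity. In Section 3.6.2 and the synopsis, state that the two confirming measurements are positive results in that assay. Assay format and cut-off can stay with the central laboratory. A matching line in Appendix 15.2 would be tidy, but its absence is not an error.

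The cost is a wording correction, one clause in two places and a few conditional laboratory assays in place of the one already planned. At two measurements per affected subject, and on an assumed range of 0 to 3 affected among the 12 continuing, that is 0 × 2 = 0 to 3 × 2 = 6 assays. Stored backup samples from Segments 1 to 3 can be used where needed. None is required at the End of Study visit for subjects entering the treatment protocol.

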3.6.3 Withdrawal and Replacement of Subjects

Subjects will be withdrawn for the following reasons:

- The subject withdraws consent (no justification is required); and/or
- The subject develops a condition that in the investigator's opinion makes it medically necessary that the subject not continue in the study.

After a discussion between the investigator and sponsor, subjects may be withdrawn for the following reasons:

- An AE that in the investigator's or sponsor's opinion requires the subject be withdrawn from the study;
- Violation of eligibility criteria;
- Major protocol violations or deviations from the treatment plan (e.g., incorrect IMP administration);

- Lost to follow-up after all attempts at contacting the subject; and/or
- Death.

In all cases, the reasons for withdrawal will be recorded in the subject's source documentation and in the Case Report Form (eCRF). It is possible that some subjects may become lost to follow-up during the study. Every reasonable effort will be made to contact these subjects; all available efficacy and safety data collected for these subjects will be used, even if incomplete. Subjects withdrawn from the study may be replaced so that there are at least 10 evaluable subjects.

Subjects who do not meet the entry criteria at screening will be ineligible for treatment and will be deemed screen failures. Subjects who are screen failed will not receive IMP; therefore, no PK or safety data will be collected for these subjects, and only demographic information will be collected on the eCRF. Subjects who screen fail will be considered screened but not enrolled. A screen failed subject may re-enter the study if they pass the re-screening. Only subjects who qualify for treatment will be enrolled.

